### Cohort Sampling

This is a retrospective cohort study with risk-set sampling for exposure status of convalescent plasma using EHRs in the Baylor Scott & White Health (BSWH) healthcare delivery system. In brief, patients who received convalescent plasma will be matched to a similar population who did not receive convalescent plasma around the same time ( $\pm 2$  days) of transfusion across sites. The administration date of convalescent plasma for the treated population and the matched date for the untreated population are thereafter referred as the index date. The matching scheme for risk-set sampling is defined in step-by-

step points in the following paragraph. The follow-up for the matched cohort will start from the index date and continue until the end of the observation period. The observation period for this study is defined as at least 28 days from the index date. In other words, the index date must be at least 28 days prior to the date of data pull to allow for adequate follow-up and minimize selection bias from informative censoring due to death or discharge for palliative care. An unexposed patient at the index date could receive convalescent plasma during the follow-up and the follow-up will be censored at the administration date of convalescent plasma (Figure 1).

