**Figure 1. Schematic diagram for retrospective cohort study with risk-set sampling for convalescent plasma exposure**

CP= convalescent plasma

\* Hospital admission includes the earliest encounters at emergency or inpatient departments around COVID-19 confirmation within  $\pm 14$  days.

† The earliest possible date is July 1st, 2020.

Step-by-step risk-set sampling with replacement for the retrospective cohort design to account for confounding and to strategize EHR abstraction at BSWH:

1. Identify patients hospitalized with laboratory-confirmed COVID-19 (Source population)

The study population will be patients with laboratory-confirmed COVID-19 (i.e., RT-PCR test results recorded by the BSWH laboratory informatics systems and/or the EHR system) and received or matched to a patient who received convalescent plasma from July 1st to September 28th. Patients must have at least 28 days of observation opportunity from the date of data pull to the index date (reverse order). Patients cannot have been previously admitted into hospitals due to RT-PCR laboratory confirmed COVID-19.

2. Identify patients who received convalescent plasma (Exposed group)

Blood bank records will be scanned to identify patients who had at least one order to transfuse COVID-19 convalescent plasma using the International Society of Blood Transfusion (ISBT) 128 codes (Appendix 1). The order will be linked to the administration record of the plasma to determine the date and time the product was given.

3. Risk-set sampling and matching variables (Unexposed group)

For each patient who received a first dose of convalescent plasma, we will sample from the source population who did not receive convalescent plasma (Unexposed group) at the same calendar time ( $\pm 2$  days) and match on the following variables. One patient could be sampled at maximum twice; first sampled into the unexposed group and later sampled into the exposed group due to initiation of convalescent plasma transfusion during follow-up.

- Calendar date around the index date within  $\pm 2$  days: Risk-set sampling to match exposed and unexposed patients will account for this factor
- Age ( $\pm 5$  years)
- Sex (female, male)
- Days from hospital admission to the index date

4. Propensity score matching and baseline covariates

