The propensity score is defined as the probability of a patient receiving convalescent plasma conditioned on their observed baseline covariates. Baseline is defined as the period prior to and including the index date. Baseline covariates for the propensity score modeling is listed below and further defined in Appendix 2. To account for confounding by baseline covariates described below, a logistic regression will be fitted to estimate the probability of receiving convalescent plasma. In the event of low frequency of certain covariates, that may cause model convergence problem, such covariates will be removed from the propensity score model. Covariates that are strongly related to convalescent plasma transfusion but only weakly related to the primary outcome will not be included in the propensity model to preserve precision of the estimates. Exposed and unexposed patients will be matched according to propensity score with nearest neighbor caliper matching algorithm without replacement with a match ratio up to 1:4 based on the power calculation (Section V. Sample Size). Propensity density plots pre- and post-matching will be evaluated for overlapping areas.

- Age (continuous)
- Race and ethnicity
- Hospital site
- Comorbidities
- Concomitant medications
- Oxygen requirements as a proxy for disease severity (Appendix 3) 4-12 hours prior to the index date

- Laboratory results: creatinine, D-dimer, troponin, absolute lymphocyte count, ferritin, C-reactive protein
- Vital signs: Respiratory rate (min), Heart rate (min), Systolic BP (mmHg), Temperature (°C)

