#### Comparative Analyses

A Kaplan-Meier curve will be plotted using the propensity score matched cohorts. To control for measured confounding, patients will be sampled in risk sets with replacement and propensity score matched. Distribution of covariates between exposure groups before and after propensity score matching will be assessed to evaluate the balance of baseline covariates and potential residual confounding. Absolute standardized differences, the differences in means or proportions divided by the pooled standard deviation, will be computed for each covariate to check its distribution balance within exposure groups. Covariates with an absolute standard difference greater than 0.1 will be further controlled in the analyses by including specific variables in the Cox model.

The adjusted incidence rates of death in the first 7, 14, 21, and 28 days after the index date will be estimated for the exposed and unexposed groups using the propensity score-matched cohort.

For the primary outcome (28-day in-hospital mortality), a Cox proportional hazards regression will estimate hazards ratios (HRs) and 95% confidence intervals (CIs) using the propensity score-matched cohort. Patients will be followed from the index date until the earliest of the following: 1) death, 2) discharge alive, 3) day 28 since the index date, or 4) the date of unexposed patients who were administered COVID-19 convalescent plasma. Patients discharged alive will be censored at the discharge date. The proportional hazards assumption will be evaluated using Schoenfeld residuals test and visual inspection of log-log plots.

For the secondary outcome of discharge alive, we will not censor the follow-up at the date of in-hospital death but will censor at day 28 to account for this worst possible outcome and to account for the competing risk of in-hospital death. In other words, patients will be followed from the index date until the earliest of the following: 1) discharge alive, 2) day 28 since the index date, or 3) the date of unexposed patients who were administered COVID-19 convalescent plasma.

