### Sensitivity Analyses

- 1) To assess the COVID-19 cohort definition of hospital admission within ±14 days of laboratory confirmed COVID-19 diagnosis, we will further restrict the source population to those who were admitted into affiliated BSWH hospitals within ±7 days of laboratory confirmed COVID-19 diagnosis. This is because COVID-19 could progress quickly and patients could also transfer to hospitals outside of the network of BSWH with a large time window around COVID-19

confirmation resulting in potential residual confounding by severity and survivor bias by prior treatment

- 2) Instead of ending the observation period at 28 days since the index date, we will continue follow-up until the end of the study period, unless an outcome event occurs earlier. Patients will be followed from the index date until the earliest of the following: 1) death, 2) discharge alive, 3) the end of the study period, or 4) the date of unexposed patients who were administrated COVID-19 convalescent plasma.
- 3) Given that mortality data after hospital discharge is limited and that patients could be discharged for palliative care due to disease worsening, the outcome “discharge alive” will be considered a competing risk for 28-day in-hospital mortality. To account for competing risk of in-hospital death and discharge alive, sub-distribution hazard ratios will be estimated from the Fine-Gray model. Cumulative incidence function will be estimated by modeling the cause-specific hazard function of all causes.

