## V. SAMPLE SIZE

To achieve 80% power for relative risk ratios of at least 0.7 for all-cause mortality, a sample size calculation was performed based on an assumed background survival rate of 0.75 over 28 days among hospitalized COVID-19 patients receiving usual care in the RCT for dexamethasone and a convalescent plasma to comparator ratio of 1:1, 1:2, 1:3 and 1:4. Using a two-sided log-rank test, estimated sample sizes are listed in **Table 1**.

The feasibility assessment found that the maximum number of patients who received convalescent plasma was 729 during April 1, 2020 to August 6, 2020, we greyed out rows in **Table 1** with required sample size surpassing the maximum and deemed those inapplicable.

**Table 1. Sample size estimates given background survival rate of hospitalized COVID-19 patients and 80% of power at a two-sided 0.05 significance level**

Total sample size	Sample size for convalescent plasma	Match ratio	Relative risk ratio
1,000	500	1:1	0.71
1,500	750	1:1	0.76
2,000	1,000	1:1	0.79
2,500	1,250	1:1	0.81
1,000	333	1:2	0.68
1,500	500	1:2	0.74
2,000	666	1:2	0.77
2,500	833	1:2	0.80

Total sample size	Sample size for convalescent plasma	Match ratio	Relative risk ratio
1,000	248	1:3	0.65
1,500	372	1:3	0.71
2,000	496	1:3	0.75
2,500	620	1:3	0.78
1,000	200	1:4	0.61
1,500	300	1:4	0.68
2,000	400	1:4	0.73
2,500	500	1:4	0.76

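### Discharge alive: deaths stay at risk to day 28 while living unexposed patients leave at crossover, which pushes the hazard ratio modestly above 1 even with no effect and random crossover

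*Protocol*

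**What the plan says.** Under Comparative Analyses, the paragraph on discharge alive states that "we will not censor the follow-up at the date of in-hospital death but will censor at day 28". The stated reasons are to treat death as the worst outcome and to allow for its competing risk. Follow-up then ends at the earliest of "1) discharge alive, 2) day 28 since the index date, or 3) the date of unexposed patients who were administered COVID-19 convalescent plasma". Death is not on that list.

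Cohort Sampling applies the crossover rule to unexposed patients only: "the follow-up will be censored at the administration date of convalescent plasma". Crossover is expected by design, because the step-by-step sampling scheme lets a patient be "first sampled into the unexposed group and later sampled into the exposed group due to initiation of convalescent plasma transfusion during follow-up".

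Two other parts of the protocol bear on the point:
- Sensitivity Analysis 3 brings in the Fine-Gray model on the ground that "the outcome “discharge alive” will be considered a competing risk for 28-day in-hospital mortality".
- Informative censoring, under Limitations, commits to an intent-to-treat analysis with fixed follow-up in which switching does not censor.

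The discharge-alive paragraph names no regression model. Cox is named for mortality just before it, and for ICU transfer and mechanical ventilation just after it.

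**The concern.** Keeping deaths at risk to day 28 is a recognised shortcut to the subdistribution hazard, but it is valid only when day 28 is the sole censoring time. The same paragraph adds a second censoring time, in one arm only, that a dead patient can never reach.

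Three patients show the effect:
- An unexposed patient who dies on day 3 is counted at risk through day 28.
- An unexposed patient still in hospital who receives plasma on day 6 leaves on day 6.
- An exposed patient who dies on day 3 is also counted through day 28, but no living exposed patient ever leaves by crossover.

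The unexposed risk set gradually fills with people who cannot be discharged, so its apparent discharge rate falls. This needs no link between crossover and prognosis, so it is distinct from the informative switching discussed under Limitations. Discharge alive is the first-listed secondary effectiveness outcome, and the artefact would read as faster discharge with plasma.

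**Working it through.** **Inputs from the protocol.** The two follow-up rules above. Usual-care deaths of 25%, from the "assumed background survival rate of 0.75 over 28 days among hospitalized COVID-19 patients". Design size from V. Sample Size ("80% of power at a two-sided 0.05 significance level") and matching "with a match ratio up to 1:4 based on the power calculation"; the Table 1 row with 500 plasma recipients and 2,500 in total gives 500:2,000.

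**Assumed, because the protocol does not state them.** Crossover rate, crossover timing, discharge rate, constant hazards, and a Cox fit.

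**The plan's own figures.** The protocol gives none for discharge alive. Table 1 concerns mortality and reproduces with the Freedman formula: for 500 + 500 the detectable relative risk is 0.709 (stated 0.71), for 500 + 1,000 it is 0.739 (0.74), and for 400 + 1,600 it is 0.727 (0.73). Nothing below depends on it.

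**Mechanism.** At a given day let A be the fraction alive in hospital and D the fraction dead but kept at risk (1 = exposed, 0 = unexposed). If the true discharge hazard r is the same in both arms, the apparent hazard in an arm is r·A/(A + D). The exposed-to-unexposed ratio is therefore

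(1 + D0/A0) / (1 + D1/A1).

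Crossover removes people from A0 but never from D0. Once deaths and random crossovers have both occurred, D0/A0 exceeds D1/A1 and the ratio exceeds 1, whatever the hazard shape.

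**One day in numbers.** Take daily hazards of 0.02 for death, 0.06 for discharge and 0.02 for crossover, at day 10:
- A1 = exp(−0.8) = 0.449; D1 = (0.02/0.08)(1 − 0.449) = 0.138
- A0 = exp(−1.0) = 0.368; D0 = (0.02/0.10)(1 − 0.368) = 0.126
- ratio = (1 + 0.126/0.368)/(1 + 0.138/0.449) = 1.344/1.306 = 1.029

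In the correct risk set, the unexposed dead carry the probability of not yet having crossed over: 0.138 × exp(−0.2) = 0.113. Then 0.113/0.368 = 0.306, the same as 0.138/0.449 up to rounding, and the ratio is 1.000.

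**Whole 28 days.** Solving the large-sample Cox score equation at 1:4, with a total exit hazard of 0.08 or 0.12 per day, a quarter of it death (22-24% deaths by day 28), and no plasma effect:

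| Unexposed who cross over | Null HR as planned | Correct risk set |
|---|---|---|
| 8-10%, spread over 28 days | about 1.02 | 1.000 |
| 14-19%, spread over 28 days | about 1.04 | 1.000 |
| 25-32%, spread over 28 days | about 1.085 | 1.000 |
| 17-33%, days 0-5 only | 1.02-1.05 | 1.000 |

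With 15% deaths and 75% discharged, the planned HR is 1.016 at 10% crossover and 1.037 at 20%. Under the null with random crossover, an analysis without crossover censoring also gives 1.000.

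**Error rate.** At 500:2,000 the standard error of log HR is about 0.06.
- HR 1.02: shift ln(1.02)/0.06 = 0.33, two-sided error about 6.3%.
- HR 1.04: shift ln(1.04)/0.06 = 0.65, two-sided error about 10%.

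A separate simulation at 500:1,000 with 25% deaths put the two-sided error at 5.8% for 10% crossover and 10.5% for 20%.

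**How much crossover can there be?** A patient may be sampled at most twice, once as unexposed and later as exposed, so each crossover is a distinct plasma recipient. With about 500 recipients and 2,000 unexposed, crossover cannot exceed 500/2,000 = 25%, and reaches that only if every recipient had first served as a control. Even 14-19% means 280-380 of the 500. Unmatched or later recipients would loosen the bound: the 729 recipients in the feasibility assessment, from a different period, would give 729/2,000 = 36%.

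**The case against.** **The net bias may not favour plasma.** A reader might infer that the planned analysis is, overall, tilted towards plasma. The protocol does not support that. Its Limitations section expects switching to be related to worsening, and censoring sicker, slower-to-discharge controls pulls the hazard ratio down. In a null simulation with an assumed 40% sicker stratum, and crossover spread over 28 days, the planned HR was 1.01-1.02 when the sicker crossed over at twice the rate of the others and 0.98-0.99 at three times the rate. With crossover in days 0-5 and a ratio of two it was 0.97-0.99. This stands: only the direction of this one artefact is established.

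**The large values are implausible.** A reader might quote 1.08 or more, with a 25% error rate at 500:2,000. That needs crossover at or above the bound just derived, at a constant rate through day 28. This stands too. At 10% crossover or less the effect is trivial, and with 20% crossover it is about 1.01 if all of it falls in days 0-3 and 1.03 if in days 0-7.

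**The protocol already has a remedy.** The intent-to-treat analysis is free of this artefact and is a commitment, not an option. That stands in part: it is offered as a check on selection bias and leaves the planned discharge analysis unchanged. Sensitivity Analysis 3 could be read as covering both outcomes, but its lead sentence concerns mortality, and it does not say that the censoring weights are arm-specific.

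**The model is not named.** True, and a separate analysis plan could supply weights. The follow-up rule is nevertheless fully stated here, and a Kaplan-Meier curve under it would be distorted in the same direction.

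**Conclusion.** The concern holds in limited form. The follow-up rule for discharge alive does not produce a valid subdistribution risk set, because it combines day-28 coding of deaths with crossover censoring that only living unexposed patients can experience. With no effect and random crossover it pushes the hazard ratio above 1: about 1.02 at 8-10% crossover, about 1.04 at 14-19% (two-sided error about 10% instead of 5% at 500:2,000), and 1.02-1.05 for 17-33% crossover in days 0-5.

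These sizes rest on assumed constant hazards, 22-24% deaths, independent patients (matched sets ignored) and an inferred Cox model. Crossover rate and timing are not in the protocol. The finding is confined to a secondary outcome. The primary mortality Cox model ends follow-up at death, so this artefact does not arise there. The rule should be corrected because it is wrong as written and cheap to repair, not because a large bias or a net advantage to plasma has been shown.

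**What to change.** For discharge alive, replace the day-28 coding of deaths with a Fine-Gray model in which in-hospital death is the competing event. Use inverse-probability-of-censoring weights for crossover, estimated separately by exposure arm; a pooled censoring curve would be wrong because only one arm can cross over. If switching is thought to be informative, include baseline prognostic covariates in the weight model, since weights that ignore prognosis leave that bias untouched. State the model by name.

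Use the same arm-specific weights in the Fine-Gray model of Sensitivity Analysis 3. Keep the day-28 coding only in the intent-to-treat analysis, where crossover does not censor, and report that result for discharge alive beside the weighted one. Also report how many unexposed patients crossed over and when, so that readers can judge how much the choice matters.

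The cost is a sentence or two in the analysis section, a little more programming and a slightly larger standard error. No new data are needed.

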### Exposure

COVID-19 convalescent plasma will be identified with ISBT-128 code (Appendix 1) in local Blood Bank data. First exposure to convalescent plasma is of interest for patients who received multiple doses. Patients can receive convalescent plasma any time during the hospital stay associated with the COVID-19 diagnosis.

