A Cox proportional hazards regression will estimate HRs and 95% CIs using the propensity score-matched cohort for the secondary outcomes of ICU transfer and mechanical ventilation. Patients will be followed from the index date until the earliest of the following: 1) the outcome of interest, 2) death, 3) discharge alive, 4) day 28 since the index date, or 5) the date of unexposed patients who were administered COVID-19 convalescent plasma.

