### Secondary Analyses

- 1) If sample size allows, stratify analyses by mechanical ventilator use prior to or at the index date
- 2) If sample size allows, subgroup analyses comparing patients who received convalescent plasma and remdesivir, with those who only received remdesivir.
- 3) If sample size allows, stratify analyses by time interval from hospital admission to the index date (<72 hours vs. ≥72 hours).
- 4) If sample size allows, stratify analyses by disease severity measured by oxygenation.

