### Appendix 3. Oxygen requirements as a proxy for disease severity (listed from lowest to highest disease severity)

- Room air
  - No documentation of the other categories listed below
- Basic oxygenation
  - Includes: Simple face mask, nasal cannula, CPAP/Bubble CPAP, T-piece, blow by, nasal prongs, open oxygen mask, tracheostomy collar, venturi mask system (if FiO2 % is < 45%), face tent (if FiO2 % is < 45%; up to 6L), nasal cannula with reservoir (i.e. oximizer; if FiO2 % is < 45%; up to 6L)
- Advanced oxygenation
  - Includes: High flow nasal cannula (HFNC), BiPAP/NPPV/NIV, Vapotherm, blender system, high flow mask, manual resuscitator, non-rebreather mask (NRB), Oxyhood, partial rebreather mask, venturi mask system (if FiO2 % is ≥ 45%), face tent (if FiO2 % is ≥ 45%; ≥ 7L), nasal cannula with reservoir (i.e. oximizer; if FiO2 % is ≥ 45%; ≥ 7L)
- Invasive ventilation
  - Transtracheal catheter, Invasive mechanical ventilation vent mode
    - CPT code 94002 (mechanical ventilation for initial day), 94003 (subsequent day), 94004 (per day)
- ECMO

NOTE: In cases where clinical flow sheets do not contain sufficient information to classify the level of oxygen support, categorization will be based on clinician review of the electronic health record

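### The ICU-transfer and mechanical-ventilation models include patients already in that state at the index date, and ICU status at index is neither matched nor balance-checked

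*Protocol*

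**What the plan says.** Protocol Section IV, Comparative Analyses, estimates hazard ratios "using the propensity score-matched cohort for the secondary outcomes of ICU transfer and mechanical ventilation". Follow-up runs from the index date to the earliest of "1) the outcome of interest, 2) death, 3) discharge alive, 4) day 28 since the index date", or the date on which an unexposed patient receives plasma. Study Outcomes lists the two outcomes by name only and does not say that they must be new or first.

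The cohort is not limited to patients outside ICU or off the ventilator:

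- The source population in Cohort Sampling, step 1, is all hospitalized patients with laboratory-confirmed COVID-19.
- Under Exposure, "Patients can receive convalescent plasma any time during the hospital stay associated with the COVID-19 diagnosis".
- Appendix 3 has baseline categories for invasive ventilation ("Transtracheal catheter, Invasive mechanical ventilation vent mode") and for ECMO.
- Secondary Analyses, item 1, reads "If sample size allows, stratify analyses by mechanical ventilator use prior to or at the index date"; item 4 stratifies by oxygenation on the same condition.

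The severity covariate in the propensity score is "Oxygen requirements as a proxy for disease severity (Appendix 3) 4-12 hours prior to the index date", and Covariates specifies the worst value in that window. Comparative Analyses adds to the Cox model any covariate with an absolute standardized difference above 0.1. ICU status at the index date appears in none of the matching variables, the propensity score list or Appendix 2.

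**The concern.** A patient who is already ventilated cannot be newly ventilated, and a patient already in ICU cannot be newly transferred there. Kept in the risk set, such patients add time at risk but no events. If their share differs between exposed and unexposed patients, the hazard ratio moves even when plasma has no effect on progression.

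Other readings of the outcomes do not rescue the analysis. If reintubation or ICU readmission counts, the model mixes first and repeat events. If baseline status is scored as an event on day 0, a state that preceded the transfusion is attributed to it. At stake is whether these two secondary results can be read as effects on worsening.

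**Working it through.** **The plan's own figures.** The protocol gives no sample size, event rate or baseline share for either outcome. Table 1 sizes mortality only. All 16 of its rows reproduce with the Freedman log-rank formula if the ratio is read as a ratio of 28-day death risks, but it does not bear on this point.

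**Are patients already in the outcome state included?** For ventilation, yes: Appendix 3 classifies it at baseline and Secondary Analyses plans to stratify on it. For ICU it is an inference. No section says so outright, but ventilated and ECMO patients are included and no ICU exclusion exists.

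**Inputs for the size (all assumed; none is in the protocol).** Hazard of the new event λ = 0.006 per day among patients at risk; exit by death or discharge μ = 0.12 per day if at risk and ν = 0.05 per day if already in the state; follow-up of 28 days; true hazard ratio 1.00. The shares already in the state are f1 (exposed) and f0 (unexposed).

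**Formulas.** For group g:

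- at risk: A_g(t) = (1 − f_g)·exp(−(λ+μ)t)
- in the risk set but not at risk: B_g(t) = f_g·exp(−νt)
- total risk set: Y_g = A_g + B_g
- event rate seen by the model: λ·A_g/Y_g

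The large-sample Cox estimate θ solves ∫[e1 − (e1+e0)·θY1/(θY1+Y0)]dt = 0 with e_g = λA_g, each group weighted by its size.

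**Hand check at 25% versus 15%.** On day 0 the ratio of event rates is 0.75/0.85 = 0.88. On day 7, exp(−0.126×7) = 0.414 and exp(−0.05×7) = 0.705:

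- exposed: 0.75×0.414 = 0.3105 and 0.25×0.705 = 0.1762, so the at-risk share is 0.3105/0.4867 = 0.638
- unexposed: 0.85×0.414 = 0.3519 and 0.15×0.705 = 0.1058, so the share is 0.3519/0.4577 = 0.769
- ratio: 0.638/0.769 = 0.83

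The imbalance grows over time because patients already in the state leave the risk set more slowly.

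**Standardized difference** = (f1 − f0)/√{[f1(1−f1) + f0(1−f0)]/2}. For 22% versus 18%: 0.04/√[(0.1716+0.1476)/2] = 0.04/0.3995 = 0.10. For 25% versus 15%: 0.10/√[(0.1875+0.1275)/2] = 0.10/0.397 = 0.25.

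| Already in state, exposed vs unexposed | Standardized difference (absolute) | Hazard ratio read when truth is 1.00 |
|---|---|---|
| 20% vs 20% | 0 | 1.00 |
| 22% vs 18% | 0.10 | 0.93 |
| 18% vs 22% | 0.10 | 1.08 |
| 25% vs 15% | 0.25 | 0.82 |
| 15% vs 25% | 0.25 | 1.21 |

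The results are the same to two decimals at match ratios 1:1 and 1:4.

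**Sensitivity to the hazards.** With no exits, a 1:4 ratio and a 28-day risk of 20–30% among unexposed patients at risk, 30% versus 20% reads about 0.86–0.87 and the reverse about 1.16. With equal shares of 10–40%, a true 0.70 reads 0.703–0.716.

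**Which rows apply to which outcome?** Ventilation at baseline is a measured covariate. A standardized difference of 0.25 would bring it into the Cox model, so the 0.10 rows mark the limit, provided the difference is computed for the ventilated category. ICU status is not measured as a covariate, so the 0.1 rule cannot act on it and the 0.25 rows remain possible.

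**The case against.** The strongest reply is that the protocol already controls baseline ventilation: oxygen support is in the propensity score, balance is checked, and imbalance above 0.1 is adjusted. This stands for ventilation. In simulation, adding baseline ventilation to the model returned 0.99 to 1.02 at imbalances of 10 to 15 points. A reader might infer that ventilation hazard ratios as far off as 0.82 or 1.21 would be reported; the adjustment rule does not support that. One gap remains: the 4–12 hour window misses an intubation in the last 4 hours before index.

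Second, the stratifications by ventilator use and by oxygenation partly answer the point, and the non-ventilated stratum approximates the analysis wanted for ventilation. Both are conditional on sample size, leave the main analysis set unchanged, and do not address ICU.

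Third, oxygen level, vital signs and laboratory values limit ICU imbalance indirectly. That is fair, but the protocol has no means of showing that they succeed.

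Fourth, outcome definitions may be completed in Appendix 4 or a separate SAP. A definition there could settle what counts as an event, but the analysis set and follow-up rule are fixed in the protocol text.

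Two further inferences should be resisted. Including such patients would dilute a reported incidence, but the protocol plans no incidence for these outcomes; it plans incidence for death and, in HIV patients, also for discharge alive. A reader might also infer that omitting ICU status biases the mortality result. Oxygen support is the chosen severity proxy, residual confounding is acknowledged under Limitations, and nothing in the protocol allows an effect on mortality to be sized.

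**Conclusion.** The point holds for two secondary outcomes and should be fixed; the at-risk problem does not touch the primary mortality analysis. As written, both hazard ratios mix patients at risk with patients already in the outcome state.

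For ventilation the distortion is modest, because the balance rule caps measured imbalance. For ICU transfer it is open-ended: nothing records, matches or checks ICU status at index. The sizes rest on assumed shares and hazards, and on reading each outcome as a new event. The direction is unknown, and balanced inclusion leaves a null result at 1.00 and barely moves a true 0.70.

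**What to change.** In Comparative Analyses:

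- Define ICU transfer and mechanical ventilation as new after the index time.
- Restrict the ICU-transfer model to patients not in ICU at the index time, and the ventilation model to patients not on invasive ventilation or ECMO at the index time. Determine status at that time, not only from the 4–12 hour window.
- Re-match within each restricted set, or match exactly on baseline status, so that matched sets stay intact.
- Report the number at risk for each model.

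In Appendix 2, record ICU status at index and include it in the balance check.

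The cost is protocol wording, a subset re-match and fewer patients in two secondary analyses. ICU and ventilation data are already needed for the outcomes themselves.

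### In-hospital death is censored in the ICU-transfer and ventilation models and no planned analysis treats it as a competing event, so these cause-specific hazard ratios can mislead if read alone as effectiveness

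*Protocol*

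**What the plan says.** Under Study Outcomes, the Protocol lists ICU transfer and mechanical ventilation as secondary effectiveness outcomes. Comparative Analyses specifies Cox models "for the secondary outcomes of ICU transfer and mechanical ventilation", with follow-up to the earliest of "1) the outcome of interest, 2) death, 3) discharge alive", day 28, or plasma given to an unexposed patient. Death without the event is thus a censoring time, on the same footing as discharge.

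For discharge alive, the same section takes another line: "we will not censor the follow-up at the date of in-hospital death but will censor at day 28". The stated reason is that death is the worst outcome and competes with discharge.

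Under Sensitivity Analyses, item 3, discharge alive "will be considered a competing risk for 28-day in-hospital mortality", and the model is described as follows: "To account for competing risk of in-hospital death and discharge alive, sub-distribution hazard ratios will be estimated from the Fine-Gray model". ICU transfer and ventilation are not named.

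Two other places touch on informative censoring. Cohort Sampling mentions death and palliative discharge, and its remedy is 28 days of observation opportunity. Limitations proposes an intent-to-treat analysis, which concerns treatment switches. Neither says how death is handled for these two endpoints.

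**The concern.** A patient who worsens and dies on the ward contributes no event to either endpoint. If such deaths are more common in one group, that group shows fewer escalations per patient at risk, and a reader may take this as benefit. Both outcomes sit under effectiveness, and nothing tells the reader that the HR is cause-specific or must be read with the hazard of death without the event.

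An imbalance is possible. Exposure is not randomised, and Limitations concedes that confounding by indication may remain. Neither the propensity covariates under Cohort Sampling nor Appendix 2 lists code status or any other limit on treatment, so matching does not balance it directly. What is at stake is the meaning of two of the three secondary effectiveness results.

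**Working it through.** **Figures in the plan.** The Protocol has no figure of its own on this point. Table 1 and the assumed 28-day survival of 0.75 concern all-cause mortality. The implied 1 − 0.75 = 25% mortality includes patients who die after ICU transfer or ventilation, and these already count as events. The share that matters, death without the event, is not given, so the shares and rates below are assumptions.

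**Set-up.** Let deterioration occur at hazard λ in the unexposed and θλ in the exposed. Each deterioration ends either in escalation (ICU transfer or ventilation) or in death without it. The share ending in death is q_U (unexposed) or q_E (exposed). Then:
- planned HR, death censored = θ(1 − q_E)/(1 − q_U)
- cause-specific HR for death without the event = θ·q_E/q_U
- HR for event or death = θ

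**Equal deterioration (θ = 1).**

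| q exposed | q unexposed | Planned HR | HR, death without event |
|---|---|---|---|
| 10% | 10% | 0.90/0.90 = 1.00 | 1.00 |
| 10% | 20% | 0.90/0.80 = 1.13 | 0.50 |
| 10% | 30% | 0.90/0.70 = 1.29 | 0.33 |
| 10% | 40% | 0.90/0.60 = 1.50 | 0.25 |
| 30% | 10% | 0.70/0.90 = 0.78 | 3.00 |

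The composite HR is 1.00 in every row, by construction.

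**With a real effect (θ = 0.70).** At 30% exposed against 10% unexposed, the planned HR is 0.70 × 0.70/0.90 = 0.54. At 10% against 30% it is 0.70 × 0.90/0.70 = 0.90.

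**Cumulative incidence at day 28.** Take λ = 0.03 and discharge 0.10 per day, θ = 1. The total probability of deterioration is (0.03/0.13) × (1 − e^(−0.13 × 28)) = 0.225 in both groups. With 30% unexposed and 10% exposed, escalation is 0.157 against 0.202, and death without it is 0.067 against 0.022. The escalation figures alone show the same ratio of 1.29. Only the pair shows that deterioration was equal.

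**Would the Protocol's other rules cure it?** A Cox simulation of 60,000 patients per scenario, with the same rates and equal deterioration, gave these HRs:

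| Handling | 10% exposed, 30% unexposed | 30% exposed, 10% unexposed |
|---|---|---|
| Death censored, as planned | 1.28 | 0.76 |
| Deaths carried to day 28 (the discharge-alive rule) | 1.39 | 0.69 |
| Deaths and discharges carried to day 28 (Fine-Gray form) | 1.31 | 0.75 |
| Event or death | 1.01 | 0.99 |

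The first row agrees with 1.29 and 0.78 to within simulation error. Neither the discharge-alive rule nor Fine-Gray removes the distortion.

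**The case against.** The strongest objection is that nothing is statistically invalid. A Cox model that censors a competing death estimates the cause-specific HR, a recognised estimand that does not need deaths to be independent of escalation. A reader might infer that the model wrongly assumes non-informative death; that does not follow. This objection stands and moves the fault from estimation to labelling and interpretation.

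The Protocol also never says that these endpoints stand for progression. That is inferred from their place under effectiveness. It gives no rate of death without escalation and does not mention ceilings of care. The mechanism is partly unmeasured confounding, which Limitations admits and for which it lists bias analyses, to be explored if feasible. All of this stands, so the size and direction in this trial are unknown.

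The composite's HR of 1.00 is built into the illustration and does not prove robustness. If patients with treatment limits also deteriorate at a different rate, the composite is confounded too.

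Deaths are not lost, since in-hospital mortality is the primary endpoint, with rates at days 7, 14, 21 and 28. This stands only in part: overall mortality does not separate deaths after escalation from deaths without it.

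Finally, extra tables may be left to a separate analysis plan. But the Protocol has its own statistical analysis section, which fixes the censoring rule for these endpoints and limits the competing-risk analysis to other outcomes.

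**Conclusion.** The point holds as a gap in what these two endpoints can support. Death is censored, no planned analysis accounts for it as a competing event, and the Protocol does account for it for discharge alive. The planned HR is valid as a cause-specific HR. Read alone as effectiveness, it can mislead in either direction: across the assumed shares it ran from 0.78 to 1.50 with no difference in deterioration, and it was 1.00 when the shares were equal.

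A reader might infer three stronger claims that the documents do not support:
- that the HRs will be biased, or biased against plasma: no share or direction is given;
- that a quarter of patients are affected: the 25% is all-cause mortality;
- that the endpoints must be replaced by composites: that is a trade-off, because it changes the secondary question and overlaps the primary endpoint.

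These are secondary endpoints, and the primary mortality analysis is unaffected.

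**What to change.** - In Comparative Analyses, keep the planned HRs for ICU transfer and mechanical ventilation and label them cause-specific.
- In Sensitivity Analyses, add two composites through day 28: ICU transfer or in-hospital death, and mechanical ventilation or in-hospital death.
- Beside each endpoint, report the cause-specific HR for death without the event; the cumulative incidence by group of the event, of death without it and of discharge alive; and the count by group of deaths without the event.
- Do not rely on extending Fine-Gray, or on the discharge-alive rule, as the only remedy.

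The cost is amendment wording, a recoded event flag and a little more analysis, since death, discharge, ICU transfer and ventilation are already study outcomes. The composites overlap the primary endpoint, and they still censor patients discharged for palliative care, a route that item 3 of Sensitivity Analyses itself recognises. Both limits should be stated with the results.
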